10.2 Adverse Events

Adverse events (AEs) will be summarized and presented using primary MedDRA System Organ Classes (SOCs) and preferred terms (PTs) according to the version of the MedDRA coding dictionary used for the study at the time of database lock. The actual version of the MedDRA coding dictionary used will be noted in the AE tables and in the clinical study report. Specific adverse events will be counted once for each subject for calculating percentages, unless stated otherwise. In addition, if the same adverse event occurs multiple times within a subject, the highest severity and level of relationship to investigational product will be reported.

10.2.1 Treatment-Emergent Adverse Events

Treatment-emergent AEs are defined as any AE with the onset that is after the first dose of study drug and with an onset date no more than 5 half-lives of the study drug (i.e., 70 days). Events where the onset date is the same as the study drug start date are assumed to be treatment-emergent, unless the study drug start time and the AE start time are collected and the AE start time is prior to the study drug start time. All treatment-emergent AEs will be summarized overall, as well as by primary MedDRA SOC and Preferred Term. The SOCs will be presented in alphabetical order, and the PTs will be presented in alphabetical order within each SOC.

The number and percentage of subjects experiencing treatment-emergent AEs will be summarized.

In the ALL_154 population, treatment-emergent AEs are defined based on the first dose of ABBV-154.

10.2.2 Adverse Event Overview

An overview of AEs will be presented consisting of the number and percentage of subjects experiencing at least one event for each of the following AE categories:

- Any treatment-emergent AE
- Any treatment-emergent AE related to study drug according to the investigator
- Any severe (CTCAE grade ≥ 3) treatment-emergent AE
- Any serious treatment-emergent AE
- Any treatment-emergent AE leading to discontinuation of study drug
- Any treatment-emergent AE leading to death
- Adverse Events of Special Interest (formally known as Safety Topics of Interest)
- All deaths
 - Deaths occurring ≤ 70 days after last dose of study drug
 - Deaths occurring > 70 days after last dose of study drug.

The overview of AEs per 100 patient-years of exposure will also be provided for the above categories.

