If a subject withdraws from study follow up or withdraws permission for the collection of their personal data, the study staff may still use available public records to obtain information about survival status only, as appropriate per local regulations.

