7.5 Statistical Analyses for Safety

All safety analyses will be performed based on the Safety Population, as defined in Section 7.1. Subjects will be analyzed based on the actual treatment received. Treatment-emergent adverse events (TEAEs), laboratory assessments, and vital signs will be summarized. Key safety variables will also be summarized on the ALL_154 Population.

A TEAE for the Safety Population is defined as an AE newly occurred or worsened after the first dose of study drug and within 70 days after the last dose of study drug. The number and percentage of subjects experiencing TEAEs will be tabulated using the MedDRA system organ class and Preferred Term, by severity, and by relationship to the study drug as assessed by the investigator. Summaries (including percentages and events per 100 patient years) of SAEs, deaths, and AEs leading to discontinuation will be provided as well. Pre-treatment AEs will be summarized separately.

For selected laboratory parameters, a listing of all subjects with any laboratory value \geq Grade 3 of the Common Toxicity Criteria will be provided. Mean change in laboratory and vital signs variables will be summarized. Additional details for the safety analysis are provided in the SAP.

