6.0 Study Drug Duration and Compliance

For the Placebo-Controlled period, LTE Period 1 and LTE Period 2, as well as study overall, duration of treatment will be summarized for each treatment group and for all ABBV-154 dose groups combined. Duration of treatment is defined for each subject as last dose date minus first dose date plus 14 days. Duration of treatment will be summarized using the number of subjects treated, mean, standard deviation, median, minimum and maximum. In addition, the number and percentage of subjects in each treatment duration interval (< 2 weeks [14 days], ≥ 2 weeks [14 days], ≥ 4 weeks [28 days], ≥ 8 weeks [56 days], ≥ 12 weeks [84 days], ≥ 24 weeks [168 days], ≥ 36 weeks [252 days], ≥ 52 weeks [364 days], ≥ 78 weeks [546 days], 104 weeks [728 days], 130 weeks [910 days], and 156 weeks [1,092 days]) will be summarized.

Treatment compliance will be summarized by treatment group and total ABBV-154 group for the safety populations. Treatment compliance is defined as the number of injections actually taken divided by the number of injections that should have been taken. All placebo injections will be included in the calculation for treatment compliance. Percent compliance will be summarized.

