10.2.4 Treatment-Emergent Adverse Events per Patient-Years of Exposure

Exposure-adjusted AEs per 100 patient-years will be provided, where AEs per 100 patient-years of exposure are defined as the number of AEs divided by the total exposure in 100 patient-years. The study drug exposure is defined as the last dose date plus $5 \times$ half-life (70 days), minus the first dose date.

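### SAP 10.2.2 asks for deaths more than 70 days after the last dose per patient-year of exposure, but exposure ends at day 70, so the late-death rate cannot be interpreted and the all-deaths rate is biased upward whenever such deaths are recorded

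*SAP*

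**What the plan says.** SAP 10.2.2 sets out an adverse event overview. Its last category is all deaths, with one sub-row for deaths up to 70 days after the last dose and another for "Deaths occurring > 70 days after last dose of study drug". Numbers and percentages are given for each category. The section then adds: "The overview of AEs per 100 patient-years of exposure will also be provided for the above categories". The death rows are not excepted.

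SAP 10.2.4 defines the rate: "patient-years of exposure are defined as the number of AEs divided by the total exposure in 100 patient-years". It also fixes the denominator. "The study drug exposure is defined as the last dose date plus" five times the "half-life (70 days), minus the first dose date".

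The only comparable duration elsewhere in the SAP, in section 6.0, closes earlier still: "Duration of treatment is defined for each subject as last dose date minus first dose date plus 14 days".

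Protocol 7.5 plans rates for deaths too, without naming a denominator: "Summaries (including percentages and events per 100 patient years) of SAEs, deaths, and AEs leading to discontinuation will be provided as well".

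**The concern.** A rate per patient-year needs events and person-time from the same risk period. The treatment-emergent rows and the row for deaths within 70 days meet that condition, because their 70-day window is the one that closes the exposure period. The late-death row and its parent row do not.

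The late-death row is not empty by design. Protocol 5.6 encourages subjects who stop study drug to keep attending scheduled visits. After withdrawal, it says, "the study staff may still use available public records to obtain information about survival status only", as local regulations allow. A late death can therefore reach the database.

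What is at stake is a mortality figure for a conjugate of an anti-TNF antibody and a glucocorticoid receptor modulator. A programmer following the SAP exactly would print one rate that has no meaning and another that mixes an open-ended numerator with a closed denominator. If dose groups differ in how many subjects stop early and stay under observation, their all-deaths rates are distorted by different amounts.

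**Working it through.** The plan states no figure to reproduce. The check is one of definitions, followed by arithmetic for the size.

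**1. Overlap of the two periods**

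- Exposure (SAP 10.2.4): first dose to last dose + 70 days.
- Risk period for a late death (SAP 10.2.2): begins after last dose + 70 days.
- Overlap: 0 days for every subject. The SAP 6.0 duration does not help, since it adds only 14 days to the last dose.

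Example with an assumed last dose at Week 28:

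- Exposure = 28 × 7 + 70 = 266 days.
- Followed to Week 78 (546 days): 546 − 266 = 280 days, or 51% of follow-up, lie outside the denominator.
- Followed to Week 182 (1,274 days): 1,274 − 266 = 1,008 days, or 79%, lie outside.

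**2. Size for the all-deaths row**

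From the documents: last planned dose at Week 180 and final visit at Week 182 (Protocol Appendix E); end of LTE Period 1 at Week 78; 70 days = 10 weeks.

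Assumed, because the documents do not say: the fraction *s* stopping early, their mean week of last dose *w*, constant mortality, and complete capture of deaths until follow-up ends at week *T*.

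Per subject, in weeks:

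- Exposure E = s(w + 10) + (1 − s)(180 + 10)
- Omitted time L = s × max(0, T − w − 10)
- Overstatement = L / E

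| s, w | E | L, T = 78 | Overstated | L, T = 182 | Overstated |
|---|---|---|---|---|---|
| 20%, Week 78 | 0.2×88 + 0.8×190 = 169.6 | 0 | 0% | 0.2×94 = 18.8 | 11% |
| 40%, Week 45 | 0.4×55 + 0.6×190 = 136.0 | 0.4×23 = 9.2 | 7% | 0.4×127 = 50.8 | 37% |
| 50%, Week 30 | 0.5×40 + 0.5×190 = 115.0 | 0.5×38 = 19.0 | 17% | 0.5×142 = 71.0 | 62% |

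**3. Both rows on a rate scale**

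Assume mortality of 0.5 per 100 patient-years and the planned 425 subjects. Of these, 10–30% have their last dose at Week 28 and the rest are dosed to Week 180, giving 180 × 7 + 70 = 1,330 days of exposure each. Worked case, 30% stopping and followed to Week 182:

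- E = 425 × (0.7 × 1,330 + 0.3 × 266) / 365.25 = 1,176.2 patient-years
- L = 425 × 0.3 × 1,008 / 365.25 = 351.9 patient-years
- Expected late deaths = 0.005 × 351.9 = 1.76
- All-deaths rate as the SAP defines it = 0.5 × (1,176.2 + 351.9) / 1,176.2 = 0.65 per 100 patient-years
- Late-death rate as the SAP defines it = 100 × 1.76 / 1,176.2 = 0.15 per 100 patient-years

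| True rate 0.50 in both rows | Followed to Week 78 | Followed to Week 182 |
|---|---|---|
| All deaths, SAP denominator | 0.51–0.54 | 0.54–0.65 |
| Late deaths, SAP denominator | 0.01–0.04 | 0.04–0.15 |
| Expected late deaths | 0.16–0.49 | 0.59–1.76 |

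The two errors run in opposite directions. The all-deaths rate is too high. The late-death figure, if read as a rate after day 70, is far too low, because everyone's earlier exposure fills its denominator. With matching person-time, all deaths over E + L and late deaths over L, both return 0.50.

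**The case against.** The strongest reply concerns size and consequence, not the definition.

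- **Follow-up to Week 182 is not established for early stoppers.** The Protocol synopsis offers LTE Period 2 to subjects who completed LTE Period 1, and Protocol 5.6 only encourages attendance off drug. This stands. It is why the Week 78 figures must sit beside the Week 182 figures.
- **Capture of late deaths may be incomplete.** Routine adverse event collection stops 70 days after discontinuation (Protocol 6.1), and checking public records is optional and subject to local rules. This stands. The bias shrinks with incomplete capture and vanishes if no late death is recorded.
- **Valid death information is already planned.** SAP 10.2.2 gives counts and percentages for every death row, the row for deaths within 70 days has a matching window, and SAP 10.2.5 lists deaths. This also stands: one rate is uninterpretable and one is mixed, but interpretable mortality data are not lost.
- **Section 10.2.4 is headed as treatment-emergent events, so it might not govern deaths.** This does not help. It is the SAP's only definition of exposure for rates. The SAP refers to the Product Safety SAP for events of special interest and vital-sign criteria, not for a death denominator. That document is not among those reviewed, so its content cannot be checked.

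A reader might also infer that differential bias follows because non-response drives early stopping. The documents do not support that. Protocol 5.4 does require non-responders to stop from Week 30, but Protocol 5.5 lists many other reasons, and no expected stopping rates are given. Nor can the Week 30 rule affect the placebo comparison, which ends at Week 12.

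**Conclusion.** The mismatch is certain from the text. The late-death rate has no time at risk in its denominator, and the all-deaths rate is biased upward whenever late deaths are recorded.

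The size is not certain. With assumed stopping rates of 20–50%, constant mortality and complete capture, the all-deaths rate is overstated by about 0–17% if early stoppers are followed only to Week 78 and by about 11–62% if all are followed to Week 182. A reader might take the higher range as the expected error. The documents do not support that, because they do not establish that early stoppers are observed through LTE Period 2. Late deaths are likely to be few.

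The consequence is limited to descriptive safety rows, mainly the long-term dose-group summaries. No hypothesis test or efficacy result is involved. The text should still be corrected, because following it exactly yields a mortality rate that cannot be interpreted.

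**What to change.** In SAP 10.2.2, state that among the death rows the exposure-based rate is given only for deaths up to 70 days after the last dose, and that all deaths and deaths beyond 70 days are shown as n (%) only. The treatment-emergent rows stay as they are. The Protocol 7.5 commitment to a death rate is then met by the row with the matching window. This costs one sentence and needs no new data, since the counts are already planned.

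If a rate for all deaths is wanted, divide by observed time from first dose (first ABBV-154 dose in ALL_154) to death, last study contact or last known survival status. Add a note that ascertainment beyond 70 days may be incomplete. This option needs an extra derived date. It should not be assumed free, because the documents do not show that a last-known-alive date is recorded systematically; where status is unknown, censor at last contact.

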10.2.3 Treatment-Emergent Adverse Events by SOC and/or PT

Treatment-emergent adverse events will be summarized by SOC and PT; by maximum relationship to study drug as assessed by the investigator (e.g., reasonable possibility or no reasonable possibility) and SOC and PT; by maximum severity and SOC and PT; and by subject number and SOC and PT. Specific adverse events will be counted once for each subject for calculating percentages unless stated otherwise. In addition, if the same adverse event occurs multiple times within a subject, the highest severity and level of relationship to investigational product will be reported.

In addition, treatment-emergent adverse events will be summarized by PT and sorted by decreasing frequency for the total ABBV-154 group.

10.2.4 Treatment-Emergent Adverse Events per Patient-Years of Exposure

Exposure-adjusted AEs per 100 patient-years will be provided, where AEs per 100 patient-years of exposure are defined as the number of AEs divided by the total exposure in 100 patient-years. The study drug exposure is defined as the last dose date plus $5 \times$ half-life (70 days), minus the first dose date.

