All adverse events reported from the time of study drug administration until 70 days after discontinuation of study drug administration will be collected, whether solicited or spontaneously reported by the subject. In addition, study procedure-related serious and nonserious adverse events will be collected from the time the subject signs the study-specific informed consent.

The following definitions will be used for Serious Adverse Reactions (SAR) and Suspected Unexpected Serious Adverse Reaction (SUSAR):

SAR Defined as all noxious and unintended responses to an investigation medicinal product (IMP) related to any dose administered that result in an SAE as defined above.

SUSAR Refers to individual SAE case reports from clinical trials where a causal relationship between the SAE and the IMP was suspected by either the sponsor or the investigator, is unexpected (not listed in the applicable Reference Safety Information) and meets one of the above serious criteria.

AbbVie will be responsible for SUSAR reporting for the Investigational Medicinal Product (IMP) in accordance with global and local requirements.

Adverse events will be monitored throughout the study to identify any of special interest that may indicate a trend or risk to subjects.

Safety Topics of Interest

The following safety topics of interest will be monitored during the study:

- Serious infections;
- Opportunistic infections;
- Active TB;
- Serious allergic reactions;
- Hypersensitivity reactions;
- Malignancies;
- Systemic glucocorticoid side effects;
- Adrenal insufficiency; and
- Iatrogenic Cushing's Syndrome.

Adverse Event Severity and Relationship to Study Drug

The investigator will rate the severity of each AE according to the National Cancer Institute Common Terminology Criteria for Adverse Events (NCI CTCAE Version 5.0).³

The investigator will use the following definitions to assess the relationship of the AE to the use of study drug:

Reasonable Possibility	After consideration of factors including timing of the event, biologic plausibility, clinical judgment, and potential alternative causes, there is sufficient evidence (information) to suggest a causal relationship.
No Reasonable Possibility	After consideration of factors including timing of the event, biologic plausibility, clinical judgment, and potential alternative causes, there is insufficient evidence (information) to suggest a causal relationship.

Pregnancy

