2.2 Study Design Overview

This is a randomized, double-blind, Phase 2b, dose-ranging study with a 12-week Placebo-Controlled Period, a 66-week Long-Term Extension (LTE) Period 1, and a 104-week LTE Period 2 in adults with moderately to severely active RA and on background MTX, who have had an inadequate response to b/tsDMARD treatment.

The Primary Analysis will be conducted after all ongoing subjects have completed Week 12 or withdrawn from the study. After the Primary Analysis, additional analyses may be conducted as needed. A final analysis will be conducted after all subjects have completed the LTE Period 2 and a safety follow-up visit 70 days after the last dose of

study drug, or have withdrawn from the study. The schematic of the study is shown in Figure 1.

Figure 1. Study Schematic

BL = Baseline; EOW = every other week; E4W = every 4 weeks; n = number of subjects; SC = subcutaneous

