10.0 Safety Analyses

10.1 General Considerations

Safety data will be summarized for each safety population (Safety_PC and ALL_154). Safety summaries will be presented by treatment group, including a total group for all subjects on active study drug. For the safety analysis, subjects are assigned to a treatment group based on the treatment actually received, regardless of the treatment randomized.

"Baseline" refers to the last non-missing observation before or on the day of the first administration of study drug or randomization if no study drug is given. Observations on the same day as the first administration of study drug will be considered for baseline,

regardless if observation time (if available) was after the first administration of study drug time.

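### SAP 10.2.4 counts 70 days after every last dose, with no cap at data cut-off, death or study exit, so ALL_154 rates per 100 patient-years are understated at any cut taken while subjects are still dosing

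*SAP*

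**What the plan says.** SAP 10.2.4 defines the rates as follows: AEs per 100 "patient-years of exposure are defined as the number of AEs divided by the total exposure in 100 patient-years". It then defines the denominator: "The study drug exposure is defined as the last dose date plus" 5 times the "half-life (70 days), minus the first dose date". SAP 10.2.2, 10.2.5 and 10.2.6 call for rates per 100 patient-years for the AE overview (deaths included), SAEs, AEs leading to discontinuation, and AESIs.

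The 70-day tail has a rationale. SAP 10.2.1 uses the same five half-lives as the window for treatment-emergent events, and Protocol 6.1 collects events over the same span: "All adverse events reported from the time of study drug administration until 70 days after discontinuation of study drug administration will be collected".

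SAP 10.1 summarises safety for both Safety_PC and ALL_154. For the latter, SAP 10.2.1 fixes the start of the numerator: "In the ALL_154 population, treatment-emergent AEs are defined based on the first dose of ABBV-154". SAP 10.2.4 says only first dose date and does not repeat that restriction.

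On timing, SAP 2.2 states: "The Primary Analysis will be conducted after all ongoing subjects have completed Week 12 or withdrawn from the study". Protocol 7.1 allows further analyses after that one. The final analysis follows LTE Period 2 and the 70-day safety visit.

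**The concern.** A rate is sound only if numerator and denominator cover the same observed time. For a subject who stopped drug and was followed for 70 days, they do. For a subject still dosing at a data cut, most of the 70 days lie after the cut: they enter the denominator, but no event on them can enter the numerator. The same holds for days after death, withdrawal of consent or loss to follow-up.

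The error always lowers the rate, so it always favours the drug. It is largest when follow-up is short. In this study that is when early rates of serious infection, adrenal insufficiency and other glucocorticoid-related events would be read to decide on later development.

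**Working it through.** The documents state no patient-years, event rate, enrolment length or dropout rate, so there is no figure of the plan's own to reproduce.

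**Inputs from the documents**
- Tail: 70 days (SAP 10.2.4).
- Dosing interval: 14 days. Administration visits are every two weeks (Protocol Appendix E), and SAP 6.0 adds 14 days to last minus first dose for all groups. I apply 14 days to the e4w arm too, since dosing is blinded.
- Allocation 1:1:1:1:1. So 80% start ABBV-154 on Day 1, and the 20% on placebo start it at Week 12 (84 days later).
- Primary Analysis: when the last ongoing subject reaches Week 12.

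**Assumptions**
- Uniform enrolment over A days.
- Constant discontinuation hazard, with stoppers followed for 70 days or to the cut.

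**Step 1: overrun per ongoing subject.** The last dose falls 0 to 14 days before the cut. Overrun = 70 − (0 to 14) = 56 to 70 days, mean 63.

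**Step 2: understatement with everyone ongoing.** Understatement = 1 − T/(T + 63) = 63/(T + 63). Mean time from Day 1 to the cut is 84 + A/2. Starting the placebo 20% at Week 12 gives T = 84 + A/2 − 0.2 × 84 = 67.2 + A/2.
- 6 months (A = 182.6): T = 158.5; 63/221.5 = 28.4%.
- 30 months (A = 913.1): T = 523.8; 63/586.8 = 10.7%.

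**Step 3: allow for discontinuation (simulation).** Mean ALL_154 days per subject, capped at the cut versus by the SAP formula:

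| Enrolment | 0% per year | 30% per year |
|---|---|---|
| 6 months | 159 vs 222 (28.4%) | 154 vs 209 (26.6%) |
| 12 months | 250 vs 313 (20.1%) | 230 vs 281 (18.2%) |
| 18 months | 341 vs 404 (15.6%) | 298 vs 345 (13.7%) |
| 24 months | 433 vs 496 (12.7%) | 359 vs 402 (10.8%) |
| 30 months | 524 vs 587 (10.7%) | 412 vs 453 (8.9%) |

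The range is about 9 to 28%. In the other direction, capped rates would be 1/(1 − 0.089) = 1.10 to 1.40 = 1/(1 − 0.284) times the rates from the SAP formula.

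**Step 4: difference between doses.** Pool about 42 switchers with the 85 original subjects in each of the 150 mg and 340 mg eow groups, with no discontinuation.
- 39 weeks of enrolment: original subjects average 84 + 136.5 = 220.5 days and switchers 136.5. The pooled mean is (2/3) × 220.5 + (1/3) × 136.5 = 192.5. Understatement is 63/255.5 = 24.7%, against 63/283.5 = 22.2% for 40 mg eow. Rate ratio distortion: 0.753/0.778 = 0.97.
- 78 weeks: the pooled mean is (2/3) × 357 + (1/3) × 273 = 329. Understatement is 63/392 = 16.1%, against 63/420 = 15.0%. Distortion: 0.839/0.850 = 0.99.

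**Step 5: final analysis.** Completers have 1,260 days (dosing to Week 180) plus an observed 70. Assume a share w leaves with a last dose at Day 630 and no later follow-up.
- w = 5%: 1 − 1,295/1,298.5 = 0.3%.
- w = 40%: 1 − 1,050/1,078 = 2.6%.

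**Step 6: which first dose.** If first dose date means first dose of any study drug, each switcher also brings 84 placebo days into the ALL_154 denominator, on average 0.2 × 84 = 16.8 days per subject, while the numerator starts only at ABBV-154.

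**The case against.** The tail itself is defensible. It matches the treatment-emergent window and the collection period, and Protocol 5.6 requires a 70-day visit, or continued visits that cover it, after drug is stopped. For subjects followed that far, the formula is right. By the final analysis that covers all completers, and subject percentages are unaffected throughout. This stands, and it confines the problem to analyses run during ongoing dosing plus a small residue at the end.

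It can also be said that neither document states that ALL_154 exposure-adjusted rates will be reported at the Primary Analysis. Protocol 7.1 describes that analysis as the final one for the Placebo-Controlled Period. This stands in part. SAP 9.5 plans efficacy summaries beyond Week 12 at that time, so LTE data will be in hand, and SAP 10.1 applies to both safety populations. Reporting ALL_154 rates then is a reasonable inference, not a stated output. Any further LTE analysis that reports these rates has the same defect.

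A programmer might cap exposure at the cut by convention. The text does not say so. The SAP refers to the product safety SAP for AESIs and some vital-sign criteria, not for exposure.

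A reader might infer two stronger points. One is that the dose trend in safety is seriously distorted because placebo switchers join only two arms. Step 4 shows that the bias is nearly uniform across doses. The other is that a single narrow percentage can be given for the Primary Analysis. It cannot, because the result depends on an enrolment length that the documents do not state.

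**Conclusion.** The definition is wrong as written for any cut taken during dosing. The overrun of 56 to 70 days per ongoing subject follows from the documents alone, and so does the direction: rates too low.

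The percentage does not follow from the documents alone. About 9 to 28% rests on 6 to 30 months of uniform enrolment, 0 to 30% yearly discontinuation, and ALL_154 rates being reported at the Primary Analysis. Shorter enrolment would give more: about 36% for 3 months without discontinuation. The final-analysis effect (about 0.3 to 2.6%, under assumed dropout) and the between-dose distortion (about 1 to 3% in the rate ratio) are minor. The documents do not support reading this as a material error in the final safety rates.

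**What to change.** Replace the exposure sentence in SAP 10.2.4 with: exposure ends at the earliest of last dose plus 70 days, death, last contact or study exit, and the data cut-off date; exposure in days is that end date minus the first dose date of the population's treatment (first ABBV-154 dose for ALL_154), plus 1.

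This needs no new data and no design change. The downside is that reported interim rates become higher, that is, less favourable. The cap at cut-off does not settle where exposure ends for Safety_PC once subjects pass Week 12; that needs its own statement.
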